### **7.4. Data sources**

The followings are data sources for the study:

1. Medical and nurse records;
2. Laboratory test results.

### **7.5. Study size**

More than 600 subjects should be observed per “Basic Standards for the Re-examination of New Medicines” (Korea MFDS notification No. 2016-97, 2016.9.6., Amendment)

### **7.6. Data management**

As used in this protocol, the term CRF should be understood to refer to either a paper form or an electronic data record or both, depending on the data collection method used in this study (“eCRF” may be used to describe an electronic data record).

A CRF should be completed for each included subject. The completed original CRFs are the sole property of Pfizer and should not be made available in any form to third parties, except for authorized representatives of Pfizer or appropriate regulatory authorities, without written permission from Pfizer.

[figure not shown]
Each study investigator has ultimate responsibility for the collection and reporting of all clinical, safety and laboratory data entered on the CRFs and any other data collection

forms (source documents) and ensuring that they are accurate, authentic / original, attributable, complete, consistent, legible, timely (contemporaneous), enduring and available when required. The CRFs must be signed by the study investigator or by an authorized staff member to attest that the data contained in the CRFs are correctly recorded. Any corrections to entries made in the CRFs, source documents must be dated, initialed and explained (if necessary) and should not obscure the original entry. For studies using electronic data capture systems, an audit trail of any corrections to original data entry must be ensured.

[figure not shown]
In many cases, the source document is the subject medical chart. In these cases, data collected on the CRFs must match the data in the chart.

In some cases (eg, subject interview), the CRF, or part of the CRF, may also serve as source documents. In these cases, a document should be available at the investigator's site as well as at Pfizer and clearly identify those data that will be recorded in the CRF, and for which the CRF will stand as the source document.

**Figure 1. Data Management Flow Chart**

**Figure 2. Data Validation Flow Chart**

## 7.7. Data analysis

### 7.7.1. Assessment of Safety and Effectiveness Parameters

#### 7.7.1.1. Analysis Populations

All analyses will be performed on the safety population, defined as those patients who took at least one dose of study medication.

#### 7.7.1.2. Safety Parameters

Safety parameters include:

[figure not shown]
- Adverse events and serious adverse events;
- Premature discontinuations from the study due to adverse events;
- Use of concomitant medications due to adverse events;
- Clinically significant abnormalities from laboratory test.

#### 7.7.1.3. Effectiveness Parameters

Effectiveness parameters include:

- Cumulative percent of patients who become pregnant over the 6 month observation period.
- Rate of the number of pregnancies per 100 per-years of follow-up.
- Change from baseline in visual analogue scale (VAS) endometriosis pain scores at each visit.

### Figure 3. Visual Analogue Scale

Source: Gerlinger C, Schumacher U, Wentzeck R, et al [10]

## 7.7.2. Statistical Considerations

Statistical analyses of safety and effectiveness parameters will be primarily descriptive in nature; no statistical hypotheses will be tested. No imputations for missing data are planned.

As required by MFDS regulations, the periodic report should be submitted to MFDS every 6 months for the first two years and then annual report should be submitted to MFDS for the third, fourth and fifth year. The final report should be submitted in the sixth year. Interim analysis will be performed in time for the report submission.

### 7.7.2.1. Safety Analyses

All safety parameters will be summarized in accordance with Pfizer Data Standards (PDS) for safety reporting. Medical histories and patient demographics will also be summarized using PDS. Selected and/or common adverse events will be further described using a 95% confidence interval for binomial proportions.

The dosage and number of injections of study medication will be summarized using descriptive statistics.

#### **7.7.2.2. Effectiveness Analyses**

- The cumulative percent of patients who become pregnant by month 6 will be calculated as  $100*(1 - \text{Kaplan-Meier curve at month 6})$ , where the Kaplan-Meier (KM) method for estimating survival function will be applied to time-to-pregnancy. Patients who did not become pregnant will be censored at the time of their last follow-up. The KM method will also be used to calculate a 95% confidence interval for this cumulative percent at month 6.
- The rate of pregnancies per 100 person-years of follow-up will be accompanied by an 95% confidence interval; this confidence interval will be based on the Poisson distribution.
- Mean change in VAS scores from baseline will be tested against zero change using the paired t-test; p-values  $\leq 0.05$  will indicate statistically significant change. Mean change will also be described using a 95% confidence interval.

Detailed methodology for summary and statistical analyses of data collected in this study will be documented in a SAP, which will be dated, filed and maintained by the sponsor. The SAP may modify the plans outlined in the protocol; any major modifications of primary endpoint definitions or their analyses would be reflected in a protocol amendment.

#### **7.8. Quality control**

Data Quality Measurement is performed by Data QC Coordinator to define the level of data quality and evaluate the data quality.

For all items, 10% Data Quality Check is conducted before the DB lock. If error rate is satisfied less than 0.05%, Data Quality Check is stopped, if not, 10% sampling and Data Quality Check is repeated. In repeated Data Quality Check, if error rate is satisfied less than 0.05%, Data Quality Check is stopped, if not, 100% Data Quality Check is made. As a result of 10% sampling, only if more than 100 subjects is sampled, Data Quality Check is conducted for 100 subjects.

CRF-to-Database Inspection outcomes will be approved by Pfizer Korea.

#### **7.8.1. Record retention**

To enable evaluations and/or audits from regulatory authorities or Pfizer, the investigator agrees to keep records, including the identity of all participating subjects (sufficient information to link records, eg, CRFs and hospital records), all original signed informed consent forms (ie, data privacy statement), copies of all CRFs, serious adverse event forms, source documents, and detailed records of treatment disposition, and adequate documentation of relevant correspondence (eg, letters, meeting minutes, telephone calls reports). The records should be retained by the investigator according to local regulations, or as specified in the Clinical Study Agreement, whichever is longer.

If the investigator becomes unavailable for any reason to continue to retain study records for the required period (eg, retirement, relocation), Pfizer should be prospectively notified. The study records must be transferred to a designee acceptable to Pfizer, such as another investigator, another institution, or to an independent third party arranged by Pfizer. The investigator must obtain Pfizer's written permission before disposing of any records, even if retention requirements have been met.

## **7.9. Limitations of the research methods**

- Regulatory- required study for maintaining license and exclusivity.
- SAP and number of enrolled subjects are ruled by PMS guideline of Korea MFDS, not specific to disease and/or drug characteristics.

## **7.10. Other aspects**

Not applicable.

# **8. PROTECTION OF HUMAN SUBJECTS**

## **8.1. Patient Information and Consent**

All parties will ensure protection of patient personal data and will not include patient names on any sponsor forms, reports, publications, or in any other disclosures, except where required by laws. In case of data transfer, Pfizer will maintain high standards of confidentiality and protection of patient personal data.

The informed consent form must be in compliance with local regulatory requirements and legal requirements.

The informed consent form used in this study, and any changes made during the course of the study, must be prospectively approved by both the IRB/IEC and Pfizer before use.

The investigator must ensure that each study patient, or his/her legally acceptable representative, is fully informed about the nature and objectives of the study and possible risks associated with participation. The investigator, or a person designated by the investigator, will obtain written informed consent from each patient or the patient's legally acceptable representative before any study-specific activity is performed. The investigator will retain the original of each patient's signed consent form.

## **8.2. Patient withdrawal**

Patients may withdraw from the study at any time at their own request, or they may be withdrawn at any time at the discretion of the investigator or sponsor for safety, behavioral, or administrative reasons. In any circumstance, every effort should be made to document subject outcome, if possible. The investigator should inquire about the reason for withdrawal and follow-up with the subject regarding any unresolved adverse events.

If the patient withdraws from the study, and also withdraws consent for disclosure of future information, no further evaluations should be performed, and no additional data

should be collected. The sponsor may retain and continue to use any data collected before such withdrawal of consent.

### **8.3. Institutional Review Board (IRB)/Independent Ethics Committee (IEC)**

It is the responsibility of the investigator to have prospective approval of the study protocol, protocol amendments, and informed consent forms, and other relevant documents, (eg, recruitment advertisements), if applicable, from the IRB/IEC. All correspondence with the IRB/IEC should be retained in the Investigator File. Copies of IRB/IEC approvals should be forwarded to Pfizer.

### **8.4. Ethical Conduct of the Study**

The study will be conducted in accordance with legal and regulatory requirements, as well as with scientific purpose, value and rigor and follow generally accepted research practices described in *Good Pharmacoepidemiology Practices* (GPP) issued by the International Society for Pharmacoepidemiology (ISPE), Good Epidemiological Practice (GEP) guidelines issued by the International Epidemiological Association (IEA).

## **9. ADVERSE EVENT REPORTING**

### **9.1. Requirements**

The table below summarizes the requirements for recording safety events on the case report form and for reporting safety events on the non-interventional study (NIS) adverse event monitoring (AEM) Report Form to Pfizer Safety. These requirements are delineated for three types of events: (1) serious adverse events (SAEs); (2) non-serious AEs (as applicable); and (3) scenarios involving drug exposure, including exposure during pregnancy, exposure during breast feeding, medication error, overdose, misuse, extravasation, and occupational exposure. These events are defined in the section “Definitions of safety events”.

Safety event	Recorded on the case report form	Reported on the NIS AEM Report Form to Pfizer Safety within 24 hours of awareness
SAE	All	All
Non-serious AE	All	None
Scenarios involving exposure to a drug under study, including exposure during pregnancy, exposure during breast feeding, medication error, overdose, misuse, extravasation; lack of efficacy; and occupational exposure	All (regardless of whether associated with an AE), except occupational exposure	All (regardless of whether associated with an AE)

For each AE, the investigator must pursue and obtain information adequate both to determine the outcome of the adverse event and to assess whether it meets the criteria for classification as a SAE (see section "Serious Adverse Events" below).

Safety events listed in the table above must be reported to Pfizer within 24 hours of awareness of the event by the investigator **regardless of whether the event is determined by the investigator to be related to a drug under study**. In particular, if the SAE is fatal or life-threatening, notification to Pfizer must be made immediately, irrespective of the extent of available event information. This timeframe also applies to additional new (follow-up) information on previously forwarded safety event reports. In the rare situation that the investigator does not become immediately aware of the occurrence of a safety event, the investigator must report the event within 24 hours after learning of it and document the time of his/her first awareness of the events.

For safety events that are considered serious or that are identified in the far right column of the table above that are reportable to Pfizer within 24 hours of awareness, the investigator is obligated to pursue and to provide any additional information to Pfizer in accordance with this 24-hour timeframe. In addition, an investigator may be requested by Pfizer to obtain specific follow-up information in an expedited fashion. This information is more detailed than that recorded on the case report form. In general, this will include a description of the adverse event in sufficient detail to allow for a complete medical assessment of the case and independent determination of possible causality. Any information relevant to the event, such as concomitant medications and illnesses must be provided. In the case of a patient death, a summary of available autopsy findings must be submitted as soon as possible to Pfizer or its designated representative.

### **9.1.1. Reporting period**

For each patient, the safety event reporting period begins at the time of the patient's first dose of Sayana® or the time of the patient's informed consent if s/he is already exposed to Sayana®, and lasts through the end of the observation period of the study, which must include at least 28 calendar days following the last administration of a drug under study; a report must be submitted to Pfizer Safety (or its designated representative) for any of the types of safety events listed in the table above occurring during this period. If a patient was administered a drug under study on the last day of the observation period, then the reporting period should be extended for 28 calendar days following the end of observation. Most often, the date of informed consent is the same as the date of enrollment. In some situations, there may be a lag between the dates of informed consent and enrollment. In these instances, if a patient provides informed consent but is never enrolled in the study (e.g., patient changes his/her mind about participation), the reporting period ends on the date of the decision to not enroll the patient.

If the investigator becomes aware of a SAE occurring at any time after completion of the study and s/he considers the SAE to be related to Sayana®, the SAE also must be reported to Pfizer Safety.

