## 7. RESEARCH METHODS

### 7.1. Study design

This study is an open-label, non-comparative, observational, non-interventional, prospective and multi-center study in which subjects administered Sayana® (administered as part of routine practice in Korean health care centers by accredited physicians) will be observed prospectively for a period of 6 months from the enrollment date. The visit schedule or interval will be decided by the investigator.

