### 7.2. Setting

Subjects will be enrolled by continuous registration method. The investigators will assess all the subjects in their practice who receive at least 1 dose of Sayana® 104mg/0.65mL agreed to participate in this study by signing the 'data privacy statement'. All subjects enrolled should meet the usual prescribing criteria for as Sayana® per the local product document and should be entered into the study at the investigator's discretion.

A written, Pfizer and institutional review board (IRB)/independent ethics committee (IEC)-approved, informed consent (ie, Data privacy statement) must be obtained before initiating study procedures.

The eligibility of the subject will be evaluated. After inclusion of the subject and after obtaining written informed consent (ie, Data privacy statement) (prior to any procedure being performed) from the subject or subject's parents/ legal representative (as appropriate), the investigator or site staff will record the subject data into source documents and into a Case Report Form (CRF). Enrollment visit is the visit when subject signs on informed consent (ie, Data privacy statement). Following the baseline data collection , the visits are at the discretion of the investigator and may follow the local usual standard of care, however, the sponsor recommends safety and treatment data

assessments at 3 month intervals (every 12~14weeks) at a minimum during the 6 months of participation. A Follow-up Call is to be conducted by investigator or delegated staffs at least 28 calendar days after the last administration of the study drug within the observational period in order to collect information on the occurrence of adverse events and concomitant medications.

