### **7.2.1. Inclusion criteria**

Patients must meet all of the following inclusion criteria to be eligible for inclusion in the study:

1. Subjects or legally authorized representatives of pediatric subjects agree to provide written informed consent form (ie, data privacy statement).

Women subjects who are initiating treatment with Sayana® for the first time as per the local product document for usage Evidence of a personally signed and dated informed consent document indicating that the patient (or a legally acceptable representative) has been informed of all pertinent aspects of the study is required.

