### **7.2.2. Exclusion criteria**

Patients meeting any of the following criteria will not be included in the study:

1. Known or suspected pregnancy.
2. Undiagnosed vaginal bleeding.
3. Known or suspected malignancy of breast.
4. Active thrombophlebitis, or current or past history of thromboembolic disorders, or cerebral vascular disease.
5. Significant liver disease.
6. Known hypersensitivity to medroxyprogesterone acetate or any of its other ingredients.
7. Women who are before menarche or who are post-menopausal.
8. Treatment with any investigational agent or device within 30 days prior to the enrollment visit.

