5.1 SAFETY ANALYSIS SET

Subject who have been administered Sayana® at least once will be included in the safety analysis set.

[figure not shown]
The following exclusions from the Safety Analysis Set are to ensure that the subjects who are not providing data to the analyses but have some record of treatment do not over-inflate the denominator for the analyses.

The following cases are excluded from the safety analysis set:

- Subjects who have taken Sayana® prior to the contract date
-
- Subjects who didn't receive Sayana® for this study
- Follow-up failure: Subjects for whom adverse event status (Adverse Events status is unknown or missing in CRF) could not be established
- Subjects who violate the inclusion/exclusion criteria (see section 2.1)
- Subjects who were prescribed for other indications except indications in the local product document:
 - [Indications]
 - Prevention of pregnancy in women of child bearing potential
 - Management of endometriosis associated pain
- Subjects who violate the dosage
 - [Dosage]
Sayana® is injected under the skin into the front upper thigh or abdomen every 3 months (12 to 14 weeks).

Unless specified otherwise, safety summaries and analyses will be presented for the safety analysis set.

PFIZER CONFIDENTIAL

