8.2.2 Efficacy Analysis

The cumulative percent of patients who become pregnant by month 6 will be calculated as $100*(1 - \text{Kaplan-Meier curve at month 6})$, where the Kaplan-Meier (KM) method for estimating survival function will be applied to time-to-pregnancy. Patients who did not become pregnant will be censored at the time of their last follow-up. The KM method will also be used to calculate a 95% confidence interval for this cumulative percent at month 6.

[figure not shown]
[figure not shown]
The rate of pregnancies per 100 person-years of follow-up will be summarized by a 95% confidence interval.

For the rate of pregnancies per 100 person-years of follow-up defined as major events, incidence rate will be calculated as follows:

$100 \times (\text{total number of patients with effectiveness endpoint}) / (\text{total person-years of patients included in the effectiveness analysis set})$ where total person-years is equal to (last evaluation date of outcome - first date of administration +1)/365.25 for all patients in the effective analysis set

The difference between the visual analogue scale (VAS) endometriosis pain scores measured at each visit and the measurement taken before the administration of Sayana[®] will be analyzed using paired t-test.

PFIZER CONFIDENTIAL

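### Person-years start at the first injection but observation starts at enrolment, and the documents do not clearly require consent by the first injection

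*Protocol*

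**What the plan says.** **Start of observation.** Protocol 7.1 says that subjects "will be observed prospectively for a period of 6 months from the enrollment date". Protocol 7.2 defines that date: "Enrollment visit is the visit when subject signs on informed consent (ie, Data privacy statement".

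**Who may enter.** Protocol 7.2.1, repeated in SAP 2.1, admits "Women subjects who are initiating treatment with Sayana® for the first time as per the local product document for usage". The first exclusion in Protocol 7.2.2 is "Known or suspected pregnancy". Protocol 7.2 also says "The investigators will assess all the subjects in their practice who receive at least 1 dose of Sayana® 104mg/0.65mL agreed to participate", which requires a dose and an agreement but does not say which comes first.

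**Women already exposed.** Protocol 9.1.1 starts safety reporting at the first dose or at "the time of the patient's informed consent if s/he is already exposed to Sayana". SAP 5.1 removes from the safety set "Subjects who have taken Sayana® prior to the contract date". Protocol 7.3.1.1 defines the contract date as that of the agreement between site and sponsor, so it is not a patient-level date. SAP 5.1 separately removes women who violate the eligibility criteria, and the efficacy set is a subset of the safety set.

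**Start of the analysis clock.** SAP 8.2.2 computes person-years from "last evaluation date of outcome - first date of administration +1)/365.25". It does not provide for late entry. It applies Kaplan-Meier to time-to-pregnancy without naming a time origin. SAP 8.2.1.2 treats all adverse events after the start of administration as on-treatment, and SAP 8.2.2 compares each pain score (VAS) with the one taken before administration.

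**The concern.** Enrolment and first injection are different dates unless a rule makes them coincide, and none is stated. Suppose a woman is injected after the site contract is signed and consents some weeks later. She passes the contract-date screen. A pregnancy recognised or suspected between injection and consent would have kept her out of the study. Those weeks therefore enter the denominator having been selected to be almost free of events, and the rate per 100 person-years looks better than it is.

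Two further results are affected for the same women. Their adverse-event reporting begins at consent, while the SAP's on-treatment period begins at the injection, so early events can be missed while the women stay in the denominator. A VAS first recorded at enrolment is also not the pre-administration value that SAP 8.2.2 calls for.

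**Working it through.** The documents give no figure to reproduce. The 600 in Protocol 7.5 is a regulatory minimum without a precision calculation, and no expected pregnancy rate is stated.

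**Inputs from the documents**
- 600 women (Protocol 7.5), used for illustration.
- 6 months (0.5 year) of observation from enrolment (Protocol 7.1).
- Person-years counted from first administration (SAP 8.2.2).
- A 95% interval based on the Poisson distribution (Protocol 7.7.2.2).

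**Assumptions**
- *s*, the share of women enrolled after their first injection, and *L*, the lag in days. Neither is given.
- Every woman is followed for the full 6 months after enrolment.
- No pregnancy is counted from the lag period.
- The one-day addition in the SAP formula is ignored on both sides.

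**Formulas**
- Person-years from enrolment: 600 × 0.5 = 300.
- Person-years by the SAP formula: 600 × (0.5 + *s* × *L*/365.25).
- SAP rate divided by the rate from enrolment: 0.5/(0.5 + *s* × *L*/365.25). This does not depend on the number of women or of pregnancies.
- Exact Poisson upper limit with no pregnancies: 100 × 3.689/person-years, where 3.689 = −ln(0.025).

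**One case in full.** With *s* = 50% and *L* = 28, 0.5 × 28/365.25 = 0.0383. Person-years are 600 × 0.5383 = 323.0 and the ratio is 0.5/0.5383 = 0.929, so the rate is 7.1% too low.

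| Share late | Lag (days) | SAP person-years | Ratio | Rate, 1 pregnancy | Rate, 3 pregnancies | Upper limit, 0 pregnancies |
|---|---|---|---|---|---|---|
| 0% | – | 300.0 | 1.000 | 0.333 | 1.000 | 1.23 |
| 10% | 14 | 302.3 | 0.992 | 0.331 | 0.992 | 1.22 |
| 25% | 28 | 311.5 | 0.963 | 0.321 | 0.963 | 1.18 |
| 50% | 28 | 323.0 | 0.929 | 0.310 | 0.929 | 1.14 |
| 50% | 91 | 374.7 | 0.801 | 0.267 | 0.801 | 0.98 |
| 100% | 91 | 449.5 | 0.667 | 0.222 | 0.667 | 0.82 |

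Rates and limits are per 100 person-years. The 91-day rows stand for women enrolled at about their second injection (the SAP gives an interval of 12 to 14 weeks). They apply only if such women are accepted.

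**Kaplan-Meier percent.** If its origin is the first injection and late entrants count as at risk from then, the same dilution occurs. If its origin is enrolment, it does not. The documents do not settle which applies.

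**The case against.** The strongest reply is that eligibility already closes the gap. Only women starting Sayana for the first time may enter, and SAP 5.1 removes violators from both analysis sets. Protocol 7.3.1.5 gives the investigator duties at the first injection, including making sure that the woman is not pregnant. This suggests that the first dose falls within the study. Section 9 reads as generic safety text (it covers paternal exposure in a study of women), so a conditional clause there does not make anyone eligible.

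Much of this stands, and it rules out three stronger conclusions that a reader might draw.

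- *That the documents permit enrolment after the first injection.* They are ambiguous, not permissive. Still, they never say how long after a first injection a woman counts as starting treatment, so the eligibility exclusion cannot be applied reproducibly to short lags. The one explicit screen on earlier exposure uses a site-level date.
- *That the time before enrolment cannot contain a counted pregnancy.* Only known or suspected pregnancy excludes. An unrecognised conception could be found later and dated by last menstrual period, which Protocol 7.3.1.5 collects.
- *That the rate is understated by 20% or 33%.* Those figures need women at a second injection, who would probably fail the inclusion criterion.

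It is also fair to say that the study is descriptive and that sampling error is much larger than the likely bias. One pregnancy in 300 person-years gives 0.333 with a 95% interval of 0.008 to 1.86. But this error runs in one direction, always favours the product, and can be removed by a rule.

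**Conclusion.** The point holds as a conditional flaw in the stated rule. Observation begins at enrolment, person-years begin at first administration, and nothing clearly makes the two coincide. For any woman enrolled late, the SAP formula adds nearly event-free time.

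For lags that the inclusion criterion might tolerate, the rate is about 0.8% too low (10% of women, 14 days) to 7% too low (50%, 28 days). With no pregnancies the rate stays at zero and only the upper limit falls, from 1.23 to between 1.22 and 1.14 per 100 person-years in those two cases. If every woman consents on or before the day of her first injection, there is no bias. The shares and lags are assumptions, and the documents cannot show whether anyone enrolled late.

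The mismatch in the adverse-event window and the post-dose VAS baseline depend on the same condition. Bias in the Kaplan-Meier percent is not shown, because its time origin is unstated. The change is worth making because it alters nothing if nobody enrolled late and removes the bias if anyone did.

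**What to change.** - **SAP 8.2.2:** start person-years and Kaplan-Meier risk time at the later of first injection and enrolment (delayed entry), and state the Kaplan-Meier time origin. Say in advance how a pregnancy is handled if its last menstrual period dates it before enrolment. Accept only a pre-injection VAS as baseline.
- **SAP 5.1:** apply the prior-exposure screen against each woman's enrolment date, with same-day injection allowed, instead of the contract date. Delayed entry then protects the rate for any already-exposed woman who is retained.
- **Reconcile** Protocol 7.2, 7.2.1 and 9.1.1 with SAP 5.1, 8.2.1.2 and 8.2.2, so that all say the same about the order of consent and first injection and about when adverse-event time starts.

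The cost is slightly fewer person-years and a slightly less favourable rate or upper limit. Women newly screened out leave the main safety summaries, but SAP 5 and 8.2.1.4 already report adverse events for excluded subjects separately. Injection dates are collected (Protocol 7.3.1.5). The enrolment date must also be in the analysis data. This should be checked, because Protocol 7.3.1.1 describes a confirmation box for consent and does not list the date as a recorded item. The SAP changes are short. Rewording the inclusion criterion itself may need a formal protocol amendment.
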